4.1 Screening data

See Protocol - Section 3.2.

4.2 Eligibility criteria

See Protocol - Section 4.2 (Table 4).

4.3 Recruitment

See Protocol - Section 4.1.

4.4 Withdrawal/loss to follow-up

The number and percentage of participants who withdraw during the study for any reason will be presented by randomised sequence.

4.5 Baseline characteristics

The following variables measured at baseline will be summarised by randomised sequence. Continuous variables will be summarised using the mean and standard deviation (SD), or median and interquartile range if the distribution is skewed. Categorical variables will be summarised using frequencies and percentages within each category.

- Age (years)
- Sex
- BMI (kg/m²)
- Systolic blood pressure (mmHg)
- Diastolic blood pressure (mmHg)
- Pulse wave velocity (m/s)
- Augmentation index (%)
- Total cholesterol (mmol/l)
- HDL cholesterol (mmol/l)
- LDL cholesterol (mmol/l)
- Triglycerides (mmol/l)
- C-reactive protein (mg/L)

5 Analysis

5.1 Outcome definitions

Primary outcomes:

- Systolic blood pressure (mmHg)
- Diastolic blood pressure (mmHg)

Secondary outcomes:

- Pulse wave velocity (m/s)
- Augmentation index (%)
- Total cholesterol (mmol/l)
- HDL cholesterol (mmol/l)
- LDL cholesterol (mmol/l)
- Triglycerides (mmol/l)
- C-reactive protein (mg/L)
- Potassium (mmol/L)
- Sodium (mmol/L)
- Urea nitrogen (mmol/L)
- Creatinine (mmol/L)
- Memory (mm)
- Processing speed (ms)
- Attention (ms)
- Executive function (mm)
- Self-rated general health (score)
- Subjective mood (score)

- Mental well-being (score)

5.2 Analysis methods

For each outcome variable, the mean and SD of the variable at each study timepoint will be reported, i.e. randomisation (visit 1), start of first intervention period (visit 2), end of first intervention period (visit 3), start of second intervention period (visit 4), end of second intervention period (visit 5), start of third intervention period (visit 6), end of third intervention period (visit 7). The mean and SD of the change in each outcome variable from the start to the end of each intervention period will also be reported.

A linear mixed effects regression model will be used to estimate the effect of each of the 2 dietary interventions with the control group and its confidence interval. Intervention group and period will be included in the model as fixed effects, and the individual identifier as the random effect. The outcome variable in the model will be the relevant measure at the end of each intervention period. This is consistent with CONSORT recommendations¹ that discourage use of change scores, and also with recommendations by Fleiss et al² and Willan and Pater³ that adjustment for baseline values of the outcome should be avoided in crossover trials.

The model assumes that the residuals, conditional on the random effect, are normally distributed. This assumption will be assessed graphically for each outcome, and if not satisfied, an appropriate transformation (e.g. log- or rank-based inverse normal transformation) for that outcome will be considered.

The model assumes that missing values are missing at random.

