Using metabolomic strategies, small, short-term intervention studies have identified potential biomarkers for citrus fruits (proline betaine) and broccoli (S-methyl-L-cysteine sulfoxide (SMSCO)) in healthy participants.^{20,21} In a large-scale epidemiologic cohort study, the PI investigated their validity by combined analyses from high quality dietary data (24-hour dietary recalls), measured BP data and 24-hr urine collections measured by NMR spectroscopy from 2,032 US and 449 UK participants. In both populations and across clinic visits, consistent and strong correlations were found for intakes of citrus fruit with proline betaine (0.72), 4-hydroxyproline betaine (0.63) and several co-metabolites (0.22-0.49) related to the same metabolic pathway and for cruciferous vegetables with S-methyl-L-cysteine sulfoxide (SMSCO, 0.39). These biomarkers will be highly valuable as objective assessment of citrus fruits and cruciferous vegetable intake, as unbiased estimates of associations with disease outcomes in large-scale epidemiological studies, and as objective measures of compliance in intervention studies.

Although meta-analyses of prospective cohort studies indicate that higher intakes of citrus fruits and cruciferous vegetables lower the risk of CVD⁸, limited evidence exists from intervention studies. Few small, acute interventions showed inconsistent findings on BP and endothelial function after supplementation of flavanones and/or orange juice²⁵⁻²⁷, while little evidence exists on cardioprotective effects of cruciferous vegetables.²⁸⁻³⁰ Based on the evidence from prospective cohort studies and recent identification of strong, specific, and validated urinary markers for these metabolites, we will test increased intakes of citrus fruits and cruciferous vegetables on vascular function in this intervention study as proof of concept to develop future, larger intervention studies. We will not only test increased intakes of citrus fruit and cruciferous vegetables against low fruit and vegetable consumption, but also against increased intakes of other fruits and vegetables to rule out the effect of the higher amount consumed.

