3.1 Study objectives and outcome measures

To assess the effect of types of plant foods on vascular function in untreated prehypertensive participants.

Primary outcome

Changes in systolic and diastolic blood pressure (mmHg) measured by automated oscillometric device (average of 3 measurements).

Secondary outcomes

Changes (end minus baseline values) in:

1. Arterial stiffness assessed by pulse wave velocity and pulse wave analysis
2. Cardiovascular risk factors measured in fasted plasma samples:

- a. Lipid profiles: total cholesterol, high-density lipoprotein cholesterol, triacylglycerides (low-density lipoprotein cholesterol will be calculated using the Friedewald formula)
- b. Insulin resistance: glucose, insulin, HbA_{1c} (HOMA-IR will be calculated using fasting glucose and insulin values)
3. Markers of endothelial function measured in fasted plasma samples (e.g. C-reactive protein)
4. Markers of low-grade inflammation measured in fasted plasma samples (e.g. Interleukin-6)
5. Urinary and circulatory metabolite profiles and individual metabolite levels
6. Established objective urinary and circulatory markers of food intake:
 - a. Fruits and vegetables: vitamin C, carotenoids, potassium, nitrate
 - b. Salt: sodium
 - c. Protein and muscle mass turnover: urea nitrogen and creatinine
7. Composition of gut microbiota to be measured from stool samples
8. Cognitive function measured by six computerised cognitive tests to assess four main cognitive domains: memory, processing speed, attention, and executive function
9. Self-rated general health and mental well-being
10. Average total, daytime, night time 24-hr ambulatory blood pressure (in subsample)
11. Average objective physical activity intensity and sleep time (in subsample)

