3.3. Dietary intervention

[figure not shown]

Figure 1: Schematic representation of the study design and clinic visits

The dietary interventions will be based on an average UK diet with similar macronutrient content:

- Control group:** 1 portion of fruits plus 1 portion of vegetables, of commonly consumed types per day. Intakes are at 25th percentile of UK consumption (NDNS) and will exclude citrus fruits, cruciferous and allium vegetables.
- Treatment 1:** 4 portions of fruits plus 4 portions of vegetables, of commonly consumed types per day excluding citrus fruits, cruciferous and allium vegetables.
- Treatment 2:** 4 portions of citrus fruits plus 4 portions of cruciferous vegetables per day.

The control group and treatment 1 will be provided with similar types of fruits and vegetables, but in different amounts, to investigate the importance of amount consumed (**Table 1**). Treatment 3 contains citrus fruits and cruciferous vegetables to test the importance of targeted types of fruits and vegetables consumed. Numbers of fruit and vegetable portions for the treatment groups are according to recommendations of the Dietary Approach to Stop Hypertension (DASH) diet.¹ Fruits and vegetables will be provided as snack, salad, cooked in mixed dishes, as 100% juice, or as soup. Allium vegetables (onion, garlic, leek, etc) will be restricted throughout the study as these vegetables also contain SMSCO. Also any other fruit or vegetable containing food will be restricted e.g., jam and fruit cakes. The diets will be matched for servings of other food groups and macronutrient balance according to average UK habitual diet. Duplicates of daily provided diets will be collected to analyse average nutritional compositions of the diet.

Meals and snacks covering 90% of daily energy needs will be delivered once a week at the participants' home according to a weekly menu cycle for each intervention sequence and accompanied by daily menus. Each day, 10% of the calorie intake is free for the participant to choose from a list of food or beverage options (to be provided by participant). This may include a maximum of one daily unit of alcohol, equalling 10 to 15 gram of ethanol. A run-in period (control diet) is to minimize the effect of habitual diet intake

before start of intervention, washout period (control diet) precedes each intervention sequence to ensure that potential cardiometabolic effects of previous diet or treatment are eliminated.

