6. STATISTICS AND DATA ANALYSIS

The statistical power calculation is based on BP-lowering effects ($-7.6 \pm 1.4 / -5.3 \pm 1.4$ mmHg) of a DASH fruit and vegetable diet (+4.5 servings/day) vs average US diet in 15 obese hypertensive participants with an average BP of 136/90 mmHg in a 3-wk cross-over study with nutritional advice (no controlled diet).³³ Assuming a conservative detectable effect size (-1 mmHg SBP) considering differences in design and type of participants, 18 participants would be sufficient to detect a difference of 1 mmHg in SBP between groups (two-sided test at 5%, SD SBP change of 1.4 mmHg, 80% power). As we use block randomisation with 6 intervention sequences, internal independent statisticians have advised to randomise a substantial number of participants per sequences. To further strengthen the study design, we will recruit and randomise (stratified by gender) 36 participants in total – with 6 participants in each group.

Treatment effects will be calculated as the changes between values at start and end of each intervention sequence. Treatment effects will be tested by comparing changes of each of the increased fruit and vegetable interventions with changes during low fruit and vegetable period (control group), and of the citrus fruit and cruciferous vegetables period with increased commonly consumed fruit and vegetable intervention. Linear mixed models will be used for repeated measures to compare changes. Treatment and period will be set as fixed effects and subject as random effect. To test for carryover effect, the previous treatment will be included in the model. Statistical significance will be set at 2-sided P-value of 0.05. The researcher performing the statistical analyses will be blinded to the treatment groups.

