Statistical Analysis Plan

The effects of types of fruits and vegetables on vascular function in prehypertensive participants: a pilot study

[figure not shown]
[figure not shown]
SAP revision history

Date	Version	Justification for SAP version
24 Jan 2022	1.1	Initial draft.
04 Feb 2022	1.2	For review.
04 Mar 2022	1.3	No comments received during review. Version for sign off

SAP responsibilities

Role in SAP development	Name	Role in trial
SAP author	[name]	Study statistician
SAP reviewer 1	[name]	Overseeing statistician
SAP reviewer 2	[name]	Principal Investigator
SAP reviewer 3	[name]	Co-Investigator
SAP reviewer 4	[name]	Co-Investigator
SAP reviewer 5	[name]	Co-Investigator
SAP reviewer 6	[name]	Co-Investigator

SAP signatures

Role	Name, affiliation	Date	Signature
Trial PI	[name]	4/3/2022	
SAP author	[name]	4/3/2022	
Overseeing statistician	[name]	4/3/2022	

1 Introduction

This document describes the primary and secondary analyses of data from a pilot study whose aim is to evaluate the effects of increased intakes of citrus fruits and cruciferous vegetables on vascular function in untreated, prehypertensive participants.

Following completion of the main trial analyses described here, further exploratory analyses of the data from this study may also be conducted. These are not part of this analysis plan.

2 Study design

See Protocol – Section 3.

ClinicalTrials.gov Identifier: NCT03410342

3 Statistical principles

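### SAP 5.2 plans two of the protocol's three diet comparisons and drops, without a reason, citrus/cruciferous versus common fruit and vegetables, the only one that isolates type from amount

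*SAP*

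**What the plan says.** Protocol section 6 sets out the treatment comparisons. Two are each increased fruit and vegetable diet against the low-intake control. The third is "of the citrus fruit and cruciferous vegetables period with increased commonly consumed fruit and vegetable intervention".

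Protocol 2.2 gives the reason for the third: citrus and cruciferous foods are tested against low intake, "but also against increased intakes of other fruits and vegetables to rule out the effect of the higher amount consumed". Protocol 3.3 says of the citrus/cruciferous diet: "Treatment 3 contains citrus fruits and cruciferous vegetables to test the importance of targeted types of fruits and vegetables consumed". The objective in Protocol 3.1 is "To assess the effect of types of plant foods on vascular function in untreated prehypertensive participants", and the SAP title is "The effects of types of fruits and vegetables on vascular function in prehypertensive participants: a pilot study".

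SAP 5.2 fits a linear mixed model with intervention group and period as fixed effects and the individual as a random effect. It uses the model to "estimate the effect of each of the 2 dietary interventions with the control group and its confidence interval". It names no other contrast. SAP 3.1 promises 95% confidence intervals for the intervention effects on all outcomes, and p-values for the primary outcomes only, with no multiplicity adjustment.

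**The concern.** The three diets form two steps. Common diet versus control changes the amount (4+4 against 1+1 portions a day) with similar types of produce. Citrus/cruciferous versus control changes type and amount together. Only citrus/cruciferous versus common changes type with the amount held at 4+4. If the analysis stops at the two control contrasts, a benefit of the citrus/cruciferous diet cannot be attributed to the foods chosen rather than to eating more of them.

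Comparing the two control results by eye does not replace the missing contrast. One interval excluding zero while the other includes it is not a test of the difference between the two diets.

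The SAP states that it covers the primary and secondary analyses and that later exploratory work lies outside it. A type comparison added after the data are seen could therefore be read as exploratory, although the protocol planned it.

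**Working it through.** **1. Comparisons, document against document**

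| Comparison | What differs | Protocol 6 | SAP 5.2 |
|---|---|---|---|
| Common vs control | amount | yes | yes |
| Citrus/cruciferous vs control | type and amount | yes | yes |
| Citrus/cruciferous vs common | type, at 4+4 portions | yes | no |

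The protocol has three and the SAP two.

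**2. Does the third enter the SAP by another route?** The SAP refers back to Protocol sections 3, 3.2, 4.1 and 4.2, but never to section 6, where the comparison is planned. No SAP section gives a reason for leaving it out. SAP 5.2 does justify another departure from the same protocol paragraph. The protocol says "Treatment effects will be calculated as the changes between values at start and end of each intervention sequence", the SAP says "The outcome variable in the model will be the relevant measure at the end of each intervention period", and the SAP cites its grounds.

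**3. The plan's own figure.** Protocol section 6 states that 18 participants suffice for a 1 mmHg difference in systolic pressure (SD 1.4, two-sided 5%, 80% power). A paired t-test reproduces this: power is 79.0% at n = 17 and 81.5% at n = 18. The calculation is not tied to one named comparison, so it gives no reason to leave the third out.

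**4. Can the planned model give the contrast, and how precisely?** It is the coefficient for citrus/cruciferous minus the coefficient for common. Let s be the within-person residual SD of the end-of-period value.

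- Complete data, 36 participants, six in each of six sequences: diet is balanced over period, so every pairwise contrast has SE = s × sqrt(1/36 + 1/36) = s × sqrt(2/36) = 0.236 s.
- Residual df = 108 observations − 36 subjects − 2 diet − 2 period terms = 68. The 95% half-width is 0.470 s.
- SAP 5.2.1 excludes six people. Assuming 36 falls to 30, with five per sequence: SE = s × sqrt(2/30) = 0.258 s, df = 90 − 30 − 4 = 56, half-width 0.517 s.
- The six exclusions can fall over the sequences in 462 ways. Across all of them, the SE of the type contrast is 0.985 to 1.016 times that of either control contrast, and 9.5% to 11.8% above its value at n = 36.
- Under assumed dropout (3, 6 or 9 of 36 stopping after one or two periods; within-person correlation 0.5, 0.7 or 0.9), the central 95% of simulated SE ratios stays within about 0.96 to 1.04.

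The documents give no s for end-of-period blood pressure, so these results are not converted to mmHg.

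**5. Cost in reported results.** SAP 5.1 lists 2 primary and 18 secondary outcomes.

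- Confidence intervals in the main analysis: 20 × 2 = 40 now, 20 × 3 = 60 with the third contrast.
- Primary p-values in the main analysis: 2 × 2 = 4 now, 2 × 3 = 6. If SAP 5.2.1 also reports them, the totals are 8 and 12.
- Expected false positives among main-analysis primary p-values if no diet had any effect: 0.05 × 4 = 0.20 now, 0.05 × 6 = 0.30.

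**The case against.** The strongest reply is that little is lost. Protocol section 6 still plans the comparison at a two-sided 0.05 level, and nothing in the SAP says it overrides that section. SAP 5.2 does not forbid the contrast, and the model contains it. With balanced data a reader could subtract the two reported estimates and attach roughly the same standard error. The study is a pilot, and the aim of testing increased citrus and cruciferous intake is partly met by the control contrast. The SAP is also silent on the protocol's carryover term, so silence here does not show a deliberate decision.

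Most of this stands, and it limits the point. Across the two documents this is an unreconciled conflict. The absence is in the SAP, and the documents do not show whether it was intended. But a contrast that readers must rebuild themselves is not planned inference, and the retained control contrast cannot answer the question for which Protocol 2.2 added the comparison. Pilot status does not explain the gap either: SAP 3.1 uses it to waive multiplicity adjustment, not to limit the contrasts.

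A narrower objection is that equal standard errors require balanced sequences as analysed, and SAP 5.2.1 says six people had their sequences mixed up. That is correct. Moving six people at random to other sequences and analysing the diets as received gave SE ratios of about 0.97 to 1.03 in 5,000 draws. Equality is then approximate, but the precision cost remains negligible.

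**Conclusion.** The concern holds and should be fixed. The protocol plans three comparisons and the SAP two, and the one left out without explanation is the only one that tests type at a fixed amount. Followed as written, the SAP produces no confidence interval for it on any outcome and no p-value for either primary outcome.

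This is a gap in pre-specification, not in the design or the model. Equal precision for the three contrasts rests on complete data and balanced sequences. Under the exclusions, dropout and mix-ups assumed above, the ratios stay within about 4% of 1. No effect in mmHg is claimed.

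**What to change.** Add to SAP 5.2:

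> From the same model, fitted to end-of-period values, the difference between the citrus/cruciferous diet and the common fruit and vegetable diet (both 4+4 portions per day) will be estimated with its 95% confidence interval for all outcomes, and with a p-value for systolic and diastolic blood pressure, including in the sensitivity analysis of 5.2.1. This is the third comparison in Protocol section 6, which states it in terms of changes.

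Name the diets rather than number them. Protocol section 1 lists the citrus/cruciferous diet as intervention 3, while Protocol 3.3 calls it Treatment 2 in the list and Treatment 3 in the text below.

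The cost is one sentence and one linear combination, with no new model or data, plus the extra unadjusted intervals and p-values counted above. If the comparison was left out deliberately, state why in the SAP and draw no conclusion about type of produce at a fixed amount.

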5.2.1 Sensitivity analysis

A sensitivity analysis on primary outcomes will be conducted by excluding 6 individuals whose randomised sequences were mixed up.

5.3 Safety data

The number and percentage of adverse events (AEs) will be reported by randomised sequence, overall and subdivided into non-serious AEs and serious AEs.

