6. STATISTICS AND DATA ANALYSIS
7. REGULATORY ISSUES
8. STUDY MANAGEMENT
9. PUBLICATION POLICY
10. REFERENCES

1. STUDY SUMMARY

- AIM** To evaluate the effects of increased intakes of citrus fruits and cruciferous vegetables on vascular function in untreated, prehypertensive participants
- DESIGN** Randomised controlled, cross-over trial with three 14-day dietary intervention periods, preceded by one week run-in period and separated by one week wash-out periods, 9 weeks in total. The diet will be fully controlled and provided by the researchers. Participants will receive in random order three interventions:
- 1: 1 portion of fruits plus 1 portion of vegetables, of commonly consumed types per day. Intakes are at 25th percentile of UK consumption and will exclude citrus fruits, cruciferous and allium vegetables.
 - 2: 4 portions of fruits plus 4 portions of vegetables, of commonly consumed types per day excluding citrus fruits, cruciferous and allium vegetables.
 - 3: 4 portions of citrus fruits plus 4 portions of cruciferous vegetables per day.
- Numbers of fruit and vegetable portions for the treatment groups are according to recommendations of the Dietary Approach to Stop Hypertension (DASH) diet.¹ Diet and macronutrient balance will be based on UK average habitual diet (NDNS). Body weight will be maintained by tailoring the diet to individual energy requirements.
- POPULATION** 36 apparently healthy men and women, aged 40 to 65 years, with upper levels of prehypertension (systolic BP 125-160 mmHg), not using antihypertensive, other cardiovascular, or diabetic medication, with a body mass index between 20 and 35 kg/m², with a habitual dietary pattern low in plant foods (≤ 4.2 portions per day) and with sufficient available food storage at home will be recruited.
- Exclusion criteria include smoking, pre-existing morbidity including diabetes mellitus, hypertension, cardiovascular or other metabolic diseases, ≥ 10 hours per week of moderate to vigorous physical activity, excessive habitual alcohol intake of >21 units per week (females) or >28 units per week, adherence to a prescribed diet, pregnancy or lactation, use of dietary supplements, food sensitivities, or vegetarian/vegan diet by choice.

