- TREATMENT** **7-day run-in/washout periods:** Participants will be asked to consume the run-in or washout (control) diet for 7 days. A run-in period is to minimize the effect of habitual diet intake before start of intervention, a washout period is to ensure that potential cardiometabolic effect of the previous intervention diet is eliminated.
- 14-day dietary intervention periods:** Participants will consume the control or intervention diet, weekly delivered at their home. Participants will be asked to visit the Cambridge Epidemiology & Clinical Trials Unit testing sites 7 times in total (every 1st and 15th day of each intervention sequence) in fasted condition.
- Day 1 and day 15 of 14-day dietary intervention periods:** Participants will be asked to arrive in fasted condition and stay at the testing site until the last measurement has been completed. Participants will bring 24-hr urine and stool collections. The following measurements will be done: anthropometrics, bioelectrical impedance, blood pressure,

pulse wave velocity, and cognitive function. Samples of fasting blood will be taken. Participants will complete questionnaires to assess maintenance of lifestyle factors e.g. physical activity and appetite profiles throughout the study. Breakfast will be provided.

DURATION Participants will be involved for 9 weeks in total:

Week 1: Run-in period

Week 2-3: 14-day dietary intervention

Week 4: Wash-out period

Week 5-6: 14-day dietary intervention

Week 7: Wash-out period

Week 8-9: 14-day dietary intervention

OUTCOME MEASURES

Primary outcome: Changes in systolic and diastolic blood pressure (mmHg)

Secondary outcomes: Changes in:

- Arterial stiffness assessed by pulse wave velocity and pulse wave analysis
- Cardiovascular risk factors measured in fasted blood samples
- Markers of endothelial function measured in fasted blood samples
- Markers of low-grade inflammation measured in fasted blood samples
- Urinary and circulatory metabolite profiles and individual metabolite levels
- Established objective urinary and circulatory markers of intakes of fruits, vegetables, and other foods
- Composition of gut microbiota
- Cognitive function
- Average total, daytime, night time 24-hr ambulatory blood pressure (in subsample)
- Average objective physical activity intensity and sleep time (in subsample)

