3.2. Study methodology

The study involves two screening moments (one screening questionnaire/interview to complete at home and one screening visit) followed by enrolment onto a 9-week randomized, placebo-controlled, cross-over intervention study. Each intervention period will be preceded by one week run-in period and separated by one week wash-out period in which participants will consume an average UK diet, low in plant foods. During the three 14-day intervention periods, participants will consume an average UK diet with increased amounts (8 servings per day) of specific types of fruits and vegetables (**Table 1**) or low in fruits and vegetables (control group, ≤ 2 servings per day). The diets will be fully controlled, provided by the researchers and delivered at the participants' home once a week. Participants will be involved for 9 weeks in total and will be invited to attend the Cambridge Epidemiology & Clinical Trials Unit testing sites 7 times in total.

Screening questionnaire/interview (15 minutes)

Consent/Screening visit (clinic visit, 2 hours)

Week 1: Run-in period

Week 2-3: 14-day dietary intervention

Week 4: Wash-out period

Week 5-6: 14-day dietary intervention

Week 7: Wash-out period

Week 8-9: 14-day dietary intervention

Screening questionnaire/interview (15 min)

Respondents will be sent by mail a screening questionnaire. Participants will be invited to complete and to return the screening questionnaire in the provided envelope to the researchers. If preferred, respondents can be contacted by telephone to assess suitability. The researchers will assess eligibility using the returned questionnaires and will contact all respondents by telephone to inform them if eligible. Eligible respondents will be sent the patient information sheet. Having read the information sheet, those who wish to continue the enrolment process will be invited to attend the Cambridge Epidemiology & Clinical Trials Unit testing sites for a consent visit and to continue screening.

Consent/screening visit (clinic, 2 hours)

Potential participants will be asked to visit the Cambridge Epidemiology & Clinical Trials Unit testing sites. The respondent will receive detailed information of the study protocol and their eligibility before obtaining informed consent. Questions and concerns will be discussed with the researchers before giving formal consent. Potential participants will then be eligible to continue the screening process.

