3.3. Study measurements

Participants will be invited to attend the Cambridge Epidemiology & Clinical Trials Unit testing sites for clinical measurements at days 1 and 15 of each intervention sequence having fasted from 10 pm the previous day. Participants will be provided with containers and instructions for urine and stool sample collection. At each clinic visit, participant will bring 24 hour urine and a stool samples that were collected on the previous day, as well as completed food checklists and a questionnaire reporting any medications or dietary supplements used during the specimen collection. The participants will be reminded by text message to complete these collections and questionnaires.

At arrival, a fasting venous blood sample will be taken with a volume that will not exceed 26 ml (156 ml for the whole study: see overview of fractions of blood samples in Table 3). Participants will be asked to void a spot urine for dipstick analyses to check pathological changes in the urine. Automated office BP, pulse wave

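### The only planned adverse-event table is by randomised sequence, so it cannot compare adverse events between diets

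*SAP*

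**What the plan says.** The safety analysis in SAP section 5.3 is one sentence: "The number and percentage of adverse events (AEs) will be reported by randomised sequence, overall and subdivided into non-serious AEs and serious AEs". Protocol sections 4.3 and 5 cover recording, individual review, definitions and expedited reporting of events. Protocol section 6 does not mention adverse events.

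On the design, Protocol section 1 states "Participants will receive in random order three interventions", and Protocol section 6 states "we use block randomisation with 6 intervention sequences", with 6 participants in each and 36 in total. Three diets have 3! = 6 possible orders, so six sequences are naturally read as all of them.

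For efficacy, SAP section 5.2 fits intervention group and period as fixed effects, so outcomes are compared by diet. SAP section 5.2.1 adds a sensitivity analysis, on primary outcomes only, "excluding 6 individuals whose randomised sequences were mixed up".

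**The concern.** Sequence is a natural grouping for baseline characteristics. It is not one for events that arise on a particular diet. Each completed sequence contains one period on each diet, so a difference between columns reflects the order of diets, dropout or chance. As written, the table cannot show whether events were more frequent on either 8-portion diet than on control, or whether the two 8-portion diets differed, although each completer is observed on all three. The SAP uses the crossover to compare diets for benefit and sets it aside for harm.

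Two details add to this. The text does not say whether the percentage is of events or of participants, or of which total. And participants whose sequences were mixed up would be listed under an order they may not have received.

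Only the summary table is affected. Review of each event as it arises (Protocol 4.3) and the Chief Investigator's judgement of relatedness for serious events (Protocol 5.3) stand.

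**Working it through.** The documents give no AE figure to reproduce. The structural step below needs no assumed risks; the illustrations do.

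**Inputs from the documents.** 36 participants, 6 sequences, 6 per sequence (Protocol 6); three 14-day diet periods, one 7-day run-in and two 7-day washouts (Protocol 1 and 3.2); 6 participants with mixed-up sequences (SAP 5.2.1).

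**Assumed inputs.** Proportion of participants with an event: 10% on control, 10% on Treatment 1, and 20%, 30% or 50% on Treatment 2. At most one event per participant per period, independent between periods.

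**1. Structure.** For completers, write each sequence as its number of periods on (control, Treatment 1, Treatment 2). All six rows are (1, 1, 1). This matrix has rank 1, so sequence totals carry only the sum of the three diet risks. A model with diet and period terms for the 18 sequence-by-period cells has full column rank (5 of 5). The design can therefore separate the diets once events are assigned to the diet at onset.

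**2. Expected counts without dropout.** Column = 6 × (sum of the three risks). Diet row = 36 × risk.

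| Treatment 2 risk | Each of the six columns | Control | Treatment 1 | Treatment 2 |
|---|---|---|---|---|
| 20% | 6 × 0.4 = 2.4 | 3.6 | 3.6 | 7.2 |
| 30% | 6 × 0.5 = 3.0 | 3.6 | 3.6 | 10.8 |
| 50% | 6 × 0.7 = 4.2 | 3.6 | 3.6 | 18.0 |

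The columns stay the same if the high risk is moved to another diet. Adding events in the run-in and two washouts, at an assumed 5% per week, gives 6 × (sum + 0.15) = 3.3, 3.9 or 5.1, again equal in all six columns.

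**3. With dropout.** Assume 10% leave after period 1 and 10% of the remainder after period 2, unrelated to events, so retention is 1, 0.9 and 0.81. At a Treatment 2 risk of 30%, the column expects:
- Treatment 2 in period 1: 6 × (0.30 + 0.09 + 0.081) = 2.83
- in period 2: 6 × (0.10 + 0.27 + 0.081) = 2.71
- in period 3: 6 × (0.10 + 0.09 + 0.243) = 2.60

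The range is 0.23; at 20% and 50% it is 0.11 and 0.46. The chance SD of one column (without dropout) is √(6 × Σp(1−p)) = 1.43, 1.53 and 1.61 for the three risks. Each diet still has 12 × (1 + 0.9 + 0.81) = 32.5 participants exposed. Dropout therefore lets very little information about diet into the sequence table.

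**4. Precision of a table by diet.** The SD of the Treatment 2 minus control count is √(36 × (0.09 + p(1−p))) = 3.0, 3.3 and 3.5. The expected differences are 3.6, 7.2 and 14.4, or about 1.2, 2.2 and 4.1 SDs.

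**5. Events outside the diet periods.** Run-in is 36 × 7 = 252 person-days and washout 36 × 14 = 504, against 36 × 14 = 504 on each diet. The total is 36 × 63 = 2268, so one third (756) lies outside the diet periods. Participants eat the control diet in those weeks, so pooling them with control would give control 504 + 756 = 1260 person-days against 504 for each other diet. The schedule ends at "Week 8-9: 14-day dietary intervention", with no washout after it. A given diet is in period 1 or 2 in 4 of 6 sequences, so it has washout follow-up in 24 of 36 participants.

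**6. Mixed-up participants.** They are 6 of 36 (17%). Moving completers between columns with equal expectation does not change the sequence table's expected counts. It would matter in a table by diet built from the randomised sequence. If control and Treatment 2 were interchanged in all 6 (an upper bound; the SAP does not say what happened), the Treatment 2 minus control difference is multiplied by 1 − 2 × 6/36 = 0.667. At 30% against 10% it falls from 20 to 13.3 percentage points. If 3 of the 6 were interchanged, the factor is 0.833.

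**The case against.** The strongest reply is that this is a 36-person pilot of ordinary foods. Harms are not a listed outcome, no estimate of effect changes, and every event is reviewed individually. That limits the importance of the point. But review of single cases does not compare frequencies, and Protocol 2.2 presents the study as groundwork for larger trials, for which AE frequency by diet is useful.

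A second reply is that small counts would limit a table by diet as well. This stands: at 20% against 10% the expected difference is only about 1.2 SDs. The table by diet would be imprecise, whereas the table by sequence is uninformative about diet whatever the size of the difference.

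Third, the mixed-up sequences do not themselves bias the planned table. This also stands. They matter for how the replacement is built.

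Fourth, the team could tabulate by diet anyway. Neither document plans it, and the handling of run-in, washout and mixed-up cases should be fixed before the events are tabulated.

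**Conclusion.** The concern holds. The planned AE table groups events by a factor along which exposure to the diets does not vary among completers, so it cannot compare diets. This follows from the design and rests on no assumed risk. Exact equality of the expected columns requires no dropout, period or carryover effects; under the assumed dropout the columns differ by at most 0.11 to 0.46 events, against a chance SD of 1.4 to 1.6. The counts by diet (for example 3.6, 3.6 and 10.8) are illustrations, because the documents give no AE risks. The loss is confined to the safety summary, and the primary and secondary analyses are untouched. It should be fixed because the correction is cheap and the trial has no other AE summary.

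**What to change.** In SAP section 5.3, add a table of AEs and serious AEs by the diet actually received at onset (control, Treatment 1, Treatment 2).

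- Give the number of events, and the number and percentage of participants with an event among those exposed to that diet.
- Use the delivered diet for the 6 mixed-up participants.
- Put run-in events in their own row, with no preceding study diet; as the protocol says, "A run-in period is to minimize the effect of habitual diet intake before start of intervention".
- Put washout events in a separate row by preceding diet, noting follow-up in 24 of 36 participants per diet. Do not pool either row with the 14-day control period.
- If onset dates were not captured, assign events by visit interval. Protocol 3.3 (Study measurements) sets "clinical measurements at days 1 and 15 of each intervention sequence", and SAP 5.2 labels the visits: "start of first intervention period (visit 2), end of first intervention period (visit 3", and so on. Visits 2–3, 4–5 and 6–7 bound the diet periods; visits 3–4 and 5–6 bound the washouts. Protocol Table 2 has no AE row, so check what was recorded at visits. The weekly telephone contacts (Protocol 3.3, Dietary intervention) may give finer timing.
- Note that small counts limit comparison between diets. The table by sequence may stay as a supplement.

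The cost is SAP wording and one descriptive table, provided that event timing and delivered diets are on record.

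A separate point affects the serious/non-serious split. Protocol 5.1 lists death among the serious criteria, while Protocol 5.2 exempts it from reporting as a serious event. The two must be reconciled. SAP 5.3 should state the definition that its serious count follows and list any event exempted from the serious-event forms. The SAP statement is only wording; a protocol change needs sponsor, ethics and Trust R&D approval (Protocol 7). The table by diet does not depend on it.
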